## Titration and Re-challenge Rules

\*\*\*PRBC transfusions allowed if at 0.15 mg/kg/d down-titrated dose level transfusions requirement remains stable within 2 units per month, and no more than 4 units total per 28 days, and patient otherwise has evidence of clinical benefit.

\* Upon re-challenge, all of the above rules reapply.

Please consult the Principal Investigator regarding dose modifications of IMG-7289 should an adverse event (AE) requiring a dose reduction occur, and also for the management of clinically significant changes in platelets, neutrophil counts, or other hematologic parameters.

### 6.3 Dosage: Additional Treatment Period

Those patients demonstrating clinical benefit in the absence of toxicity qualify for continued treatment in the Additional Treatment Period, which repeats iteratively. For qualifying patients, dose titration will continue as per the Titration Rules table (**Table 1**) above. Additional dose-titration may occur in consultation with the Principal Investigator.

### 6.4 Missed Doses

Patients who do not take their IMG-7289 dose at the usual required time should take it immediately upon noting that it was not taken; the patient should not take the dose more than 12 hours after the usual dosing time. If a patient misses a dose, they should not take two doses the following day, but should notify their study coordinator and continue with their normal daily dose the following day.

### 6.5 Dose Modification Guidelines

Adverse event intensity will be evaluated using the National Cancer Institute (NCI) Common Terminology Criteria for Adverse Events (CTCAE) version 5.0, published 27 November 2017.

Expected IMG-7289 toxicities based on non-clinical and clinical studies are reported in the latest available edition of the Investigator's Brochure.

#### 6.5.1 Hematologic Toxicities

Hematologic values outside of the normal reference range are inherent features of MPNs and are expected effects of many therapeutic attempts to manage these diseases.

Both genetic knockdown (KD) of LSD1 mRNA and pharmacologic inhibition of LSD1 show that the loss of LSD1 activity arrests the production of mature red cells, platelets and granulocytes while over-producing monocytes ([Sprussel et al., 2012](#); [Kerenyi et al., 2013](#)). Production of cells of lymphoid lineage, B and T cells is unimpaired indicating that LSD1 has very cell-specific functions and its inhibition also has very specific effects. LSD1 inhibition in malignant myeloid cells causes the induction of monocytic differentiation markers, as well as a reduction of self-renewal potential of neoplastic cells, all of which eventually result in apoptosis of treated cells. Thus, the anemia, thrombocytopenia, neutropenia and monocytosis attending LSD1 inhibition, as observed in animals treated with IMG-7289, reflect primary pharmacodynamic effects. The kinetics of anemia, thrombocytopenia, and neutropenia following complete LSD1 inhibition are a function of the lifespan of the individually affected cell types. Over the course of LSD1 inhibition, platelet and neutrophil counts are the most affected, reflecting their short mean lifespans of approximately seven and twelve days, respectively. Recovery of peripheral counts is reversible, rapid, and temporarily overshoots baseline hematologic values. At lower doses, the effects on hematopoiesis are much less pronounced suggesting that a modicum of residual LSD1 activity is sufficient to support blood cell formation. Thus, both the duration of LSD1 inhibition as well as the degree of inhibition are critical to the pharmacodynamic effects on myeloid lineages.

The intended dosing plan for ET patients is predicated on the observation that inhibition of LSD1 has a therapeutic effect when LSD1 is inhibited for a fraction of the 24-hour dosing cycle. The concentrations of IMG-7289 needed to achieve maximal effects on growth, differentiation, and apoptosis in vitro with primary

patient-derived malignant myeloid cells as well as *JAK2V617F* cell lines are similar to concentrations that *in vivo* inhibit red cell, platelet and granulocyte production. It is therefore expected that ET patients will require treatment at doses sufficient to reduce platelet counts and hemoglobin counts, respectively, and, to a lesser degree, absolute neutrophil counts. These reversible cytopenias can be managed clinically as needed with transfusions as well as broad-spectrum antibiotics in the case of febrile neutropenia as are already standard practices in the routine management of malignant myeloid diseases.

The effects of IMG-7289 on normal myeloid hematopoiesis observed in non-clinical studies are expected in humans; these are pharmacodynamic effects of LSD1 inhibition by IMG-7289, thus are not regarded as adverse. These events, with the exceptions below, will not be considered DLTs.

### 6.5.2 Dose Limiting Toxicities

DLT is defined as any one of the following AEs per CTCAE version 5.0 criteria that occurs through Day 7 of the Initial Treatment Period will be considered DLTs unless the Investigator deems the AE to be clearly unrelated to IMG-7289:

- Any Grade 3 or above thrombocytopenia associated with clinically significant bleeding\*;
- Any Grade 4 thrombocytopenia associated with a requirement for platelet transfusion;
- Any Grade 4 or 5 non-hematologic adverse event;
- Any Grade 3 or above non-hematologic adverse event with the following exceptions:
  - Nausea, vomiting or diarrhea lasting 3 days or less
  - Aesthenia lasting less than 7 days
- Any Grade 3 electrolyte abnormality unrelated to the underlying malignancy and persisting greater than 24 hours.

*\*A clinically significant bleeding event is defined as an event that is life-threatening, cannot be controlled and/or results in hemodynamic instability.*

Patients who experience DLT will have their dose adjusted downward by 50% if the Principal Investigator deems it safe for the patient to continue on IMG-7289; the titration rules will subsequently be followed. Any patient that experiences DLT that results in discontinuation of IMG-7289 therapy may begin alternative therapy within 24-48 hours of discontinuation if their physician deems this safe and appropriate regarding the resolution of the DLT.

Please consult the Principal Investigator for IMG-7289 dose modifications for the management of clinically significant changes in platelets, neutrophil counts, or other hematologic parameters.

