Physical Examinations (PE): a **Full Physical Exam**, including height, weight, vital signs and spleen measurement will be performed at Screening. **Limited Physical Exams (LPE)** will be performed weekly for 8 weeks and then monthly throughout the study, unless deemed to be needed more frequently by PI. Limited PEs include weight, vital signs, a review of body systems to assess change from previous PE, and spleen measurement. The edge of the spleen shall be determined by palpation, measured in centimeters, using a soft ruler, from the costal margin to the point of greatest splenic protrusion. The spleen should be measured in the same manner at all visits ideally by the same examiner.

Serum pregnancy testing will be performed for women of child-bearing potential (WOCBP) at Screening and pre-dose on Day 1, and if pregnancy is suspected while the patient remains on-study.

Bone marrow aspirate\* and biopsy will be performed\*\*:

- At Screening (no more than 28 days prior to the first IMG-7289 dose).
- At ITP Day 169 visit.
- Optional at approximately every 12 months thereafter, at ATP Day 169 of *every other* Additional Treatment Period (i.e., ATP2, ATP4), for as long as the patient continues to qualify for treatment.

\*Marrow from the first pull whenever possible, but no later than the second pull, is required.

\*\*The total number of bone marrow evaluations required during the Initial Treatment Phase is 2 in ~32 weeks.

Additional marrow evaluation is required only if the patient agrees to the optional time points in the Additional Treatment Phase.

Clinical laboratory measures: The following laboratory measures will be performed at Screening, pre-dose Day 1, upon suspicion of relapse, at the EoT, pre-EoS, and EoS/ET visits and in accordance with below:

- Biochemistry - monthly throughout the study (i.e., Days 29, 57, 85, 113, 141 and 169)
- Hematology with manual differential - at every clinic visit throughout the study
- C-Reactive Protein - monthly throughout the study (i.e., Days 29, 57, 85, 113, 141 and 169)

The following laboratory measures will be performed at Screening:

- Coagulation

The following laboratory measures will be performed at Screening, Week 24 and upon suspicion of relapse:

- Testing of mutant (variant) allele burden in granulocytes

Qualification Assessments:

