2. Patients taking medications that have the potential to induce or inhibit CYP3A4 or CYP2D6 should be monitored closely for potential effects of co-administration; particular attention should be given to anti-infectives in the azole class.
3. Cessation of IMG-7289 is invariably associated with a rebound in thrombopoiesis and platelet counts may easily exceed the baseline value. When IMG-7289 is discontinued, the platelet count should be monitored closely and an alternative cytoreductive therapy to lower platelets should commence within 24-48 hours.

**PROHIBITED MEDICATIONS/TREATMENTS:** The PIs will contact Imago staff with any questions pertaining to prohibited medications.

1. All cytotoxic agents, including standard-of-care therapies for ET
2. All hematopoietic growth factors: romiplostim, eltrombopag, erythropoietin (EPO), granulocyte colony stimulating factor (G-CSF) and granulocyte-macrophage colony stimulating factor (GM-CSF)
3. Monoamine oxidase A and B inhibitors
4. Anticoagulant and nonsteroidal anti-inflammatory drug (NSAID; including aspirin) use are prohibited in patients when their platelet count is  $< 50 \times 10^9/L$  (50,000/ $\mu$ L)

**Management of Study Toxicities:** Adverse event intensity will be evaluated using the National Cancer Institute (NCI) Common Terminology Criteria for Adverse Events (CTCAE) version 5.0, published 27 November 2017. Please refer to Section 8.2 for additional detail on management of study toxicities, including reduction of the starting dose based on DLT.

**Definitions:** Hematologic Toxicity: Hematologic values outside of the normal reference range are inherent features of MPNs and are expected effects of many therapeutic attempts to manage these diseases. The effects of IMG-7289 on normal myeloid hematopoiesis observed in non-clinical and clinical studies are expected in humans; these are pharmacodynamic effects of LSD1 inhibition by IMG-7289, thus are not regarded as adverse. These events, with the exceptions below, will not be considered DLTs.

Dose limiting toxicity (DLT): Any one of the following AEs that occurs through Day 7 of the Initial Treatment Period will be considered DLTs unless the Investigator deems the AE to be clearly unrelated to IMG-7289:

- Any Grade 3 or above thrombocytopenia associated with clinically significant bleeding\*;
- Any Grade 4 thrombocytopenia associated with a requirement for platelet transfusion;
- Any Grade 4 or 5 non-hematologic adverse event;

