## 7 Study Assessments and Procedures

This section provides comprehensive detail on the visits and assessments required; this section should serve as the main guidance for use during study visits. The Schedule of Events (Sections 7.7 and 7.8) contains these details in schematic form and is provided for use in a supportive/reference capacity only.

**Note:** If at any time additional clinical evaluation outside of the visit schedule is deemed necessary by the Investigator, then unscheduled visits should occur as appropriate.

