### 7.3.2 ITP Weekly Visits - Days 8, 15, 22, 29, 36, 43, 50 and 57 ( $\pm$ 1 day\*)

**\*Important:** The  $\pm$  1 day visit window applies to the visit (e.g., 'Day 8' visit may be conducted on Day 7, Day 8 or Day 9 as dictated by site and patient schedule), and not to individual assessments, unless otherwise noted for a specific assessment. To clarify, the expectation is that all required assessments will be done on a single visit day with the exception of those specifically noted below.

- Limited PE, including weight, vital signs, spleen measurement and a review of body systems to assess change from previous PE
- Adverse Events and Concomitant Medications
- Pre-dose: Blood samples for the following Local Laboratory assessments:
  - CBC with manual differential and hematology assessment to determine if dose titration is required\*\* (note: up-titration may occur no more frequently than every 4 weeks from the previous up- or down-titration; down-titration may occur at any time in the best interest of the patient)

*Important:* may be performed up to 2 days ahead of the main visit to avoid the need for IMG-7289 dispensation on the day of blood sampling. For example, if a visit is scheduled on a Wednesday,

the hematology panel and associated titration assessment can be performed Monday or Tuesday, if needed, to ensure IMG-7289 is dispensed and available for collection at the Wednesday visit.

- Collect MPN-SAF and provide questionnaire for completion on the day of the next visit, prior to or at the start of the visit
- Pre-dose: Perform drug accountability and collect study medication
- Dispense doses sufficient until the next visit and provide Dosing Card/diary
- Schedule next clinic visit

\*\*If a patient requires a dose hold, complete blood counts should be monitored at least weekly for safety and to enable re-challenge to commence as soon as counts return to the required level, if safe to do so.

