### **7.3.2.1 ITP Days 29 and 57 Only**

- Blood samples for the following Local Laboratory assessments
  - Chem-12
  - C-reactive protein

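### No scheduled post-dose chemistry falls in the seven-day DLT window, so a silent chemistry-only DLT would be found only by off-schedule testing or after an early stop

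*Combined protocol and SAP*

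**What the plan says.** **DLT definition.** The synopsis (Section 2) states: "Any one of the following AEs that occurs through Day 7 of the Initial Treatment Period will be considered DLTs". Section 6.5.2 and the Reporting Requirements in Section 11 use the same Day 7 limit. All three lists include "Any Grade 3 electrolyte abnormality unrelated to the underlying malignancy and persisting greater than 24 hours", and all three include Grade 3 or higher non-hematologic events with short exceptions. Section 11 defines an adverse event to include an abnormal laboratory finding, so an event seen only in chemistry is in scope.

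**What a DLT triggers.** Two DLTs in the first nine patients is a study stopping rule (Section 11). For the individual patient, Section 6.5.2 halves the dose if continuing is judged safe. Section 6.5.3 stops the drug if the patient then worsens, or does not improve significantly within 14 days.

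**Chemistry schedule.** The synopsis gives the on-treatment schedule as "Biochemistry - monthly throughout the study (i.e., Days 29, 57, 85, 113, 141 and 169"). Section 7.3.1.1 adds a pre-dose sample on Day 1. Among the weekly visits, the heading of Section 7.3.2.1 confines Chem-12 to "ITP Days 29 and 57 Only". Section 7.3.2 lists only a CBC for the other weekly visits, and the schedule table in Section 7.7 agrees.

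**Other routes to a chemistry result.** Section 7 says that if the Investigator thinks further evaluation is needed, "then unscheduled visits should occur as appropriate". The end-of-treatment and early-termination visits include Chem-12 (Sections 7.6.1 and 7.6.3).

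**The concern.** The electrolyte criterion is a laboratory criterion with a duration clause, yet no scheduled sample could show that it was met. An event with symptoms would surface through adverse event reporting, and the thrombocytopenia DLTs involve bleeding or transfusion and are backed by the CBC. An abnormality without symptoms gives nobody a reason to order a test.

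Three things follow. For this class of event, a count of zero or one DLT in the first nine patients does not show absence, because the event was not routinely looked for. The dose reduction and the 14-day follow-up rule cannot start for an event that nobody has seen. And the patient would normally keep taking the drug until about Day 29 before routine chemistry showed the problem.

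**Working it through.** The plan states no figure on this point. The check sets the sampling dates against the window.

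**Inputs**
- DLT window: first dose on Day 1 through Day 7 ("occurs through Day 7 of the Initial Treatment Period", Section 6.5.2).
- Day 8 visit: Section 7.3.2 says it "visit may be conducted on Day 7, Day 8 or Day 9 as dictated by site and patient schedule". The other weekly visits also have a window of ±1 day.
- Early draw: in Section 7.3.2 the CBC "may be performed up to 2 days ahead of the main visit". This applies to the hematology panel, not to Chem-12.
- Pre-dose findings are baseline events, not adverse events (Section 11), so the Day 1 chemistry cannot show a DLT.
- Assumption: Chem-12, labelled CMP in Section 7.7, includes the electrolytes. The documents do not list its components.

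**Scheduled blood samples up to the first post-dose chemistry**

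| Time point | Possible days | Chem-12 | CBC |
|---|---|---|---|
| Day 1, pre-dose | 1 | yes (baseline) | yes |
| Day 1, post-dose | 1 | no | no |
| Day 8 visit | 7 to 9 | no | yes |
| Day 15 visit | 14 to 16 | no | yes |
| Day 22 visit | 21 to 23 | no | yes |
| Day 29 visit | 28 to 30 | yes | yes |

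**Results**
1. Post-dose Chem-12 samples in Days 1 to 7: 0. A Day 8 visit held on Day 7 does not change this, because no chemistry is drawn at it.
2. First routine post-dose chemistry: 29 ± 1, so Days 28 to 30. Gap after the window closes: 28 − 7 = 21 to 30 − 7 = 23 days.
3. Visits with a CBC but no chemistry before then: Days 8, 15 and 22, so 3.
4. Days on which the Day 8 CBC can be taken: 7 − 2 = 5 through 9, so Days 5 to 9.

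**Other chemistry time points.** The suspected-relapse visit includes Chem-12, but relapse can only follow remission (Section 7.5), which must last at least 12 weeks (Appendix 12.4), so it cannot fall by Day 7. Dose-hold visits require blood counts only (Section 6.5.4). That leaves unscheduled testing and an early stop.

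**Why the effect on the stopping rule is not quantified.** Let p be the true DLT rate, f the share of DLTs detected, and q = p × f. The chance of two or more detected DLTs in nine patients is 1 − (1 − q)^9 − 9q(1 − q)^8. With p assumed to be 20%, this is 0.564 for f = 1, 0.225 for f = 0.5 and 0 for f = 0. The documents give neither p nor f, so this range reflects the assumptions and says nothing about the size of the effect in this trial.

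**The case against.** The best case for the plan has four parts.

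- **The affected events are few.** An event must be Grade 3 or higher, visible only in chemistry, without symptoms, and present within seven days at the starting dose. An electrolyte event must also last more than 24 hours. The synopsis reports 85 patients already treated. Sections 3.2 and 3.5 report no safety signals up to 6 mg/kg/d, which is 6 / 0.6 = 10 times the starting dose, and Section 3.5 places the primary effects in the bone marrow.
- **Other safeguards exist.** Adverse events are reviewed continuously by the Principal Investigator and quarterly by the DSMB. Three or more of the same event go to the DSMB outside that cycle. Enrollment is held after nine patients until the DSMB recommends continuing; because response is judged at Week 24, patients who complete the ITP will have had six routine on-treatment chemistries. The discontinuation rule for Grade 4 non-hematologic events has no Day 7 limit (Section 6.5.3).
- **Day 29 is a sensible day.** Section 3.5 infers a steady state between Days 21 and 28, and Day 29 is the first day on which up-titration is allowed.
- **Moving the whole window would be worse.** A window ending at the Day 8 visit would vary between patients and change every type of DLT.

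Most of this stands, and it keeps the point small. It does not close the gap. Reviewers cannot see a value that was never measured. A persistent abnormality found on Day 29 would be acted on, but its onset could not be dated to the first week; a transient one would be lost. The argument for Day 29 supports a sample on that day. It does not explain a laboratory DLT criterion that ends on Day 7. The last objection is right and shapes the fix.

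A reader might infer that the two-in-nine rule cannot work, or that early safety is unmonitored. The documents do not support either reading. Symptomatic and thrombocytopenic DLTs remain detectable, each weekly visit includes an examination, an adverse event review and a CBC, and testing off schedule is allowed.

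**Conclusion.** The point holds as a minor surveillance gap. One named DLT criterion, and the silent chemistry-only part of another, have no scheduled measurement inside the window to which they apply: 0 post-dose samples, with the first one 21 to 23 days after the window closes. The schedule facts are certain; the synopsis, Section 7 and the schedule table agree.

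The consequence is much less certain. How often the gap would change the DLT count cannot be estimated, because the documents give no rate for such events, and the earlier experience they describe suggests that it would be rare. The later chemistries, the three-event rule and the enrollment hold are partial safeguards that cannot place an event in the window. The conclusion assumes that Chem-12 measures electrolytes and that sites follow the schedule without adding chemistry of their own. This calls for a cheap improvement and does not undermine the design.

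**What to change.** 1. Add Chem-12 to the Day 8 visit, drawn no earlier than Day 7 and so on Days 7 to 9. Edit the laboratory list in the synopsis, the visit list in Section 7.3.2 and the table in Section 7.7. The lower limit matters: a sample taken with an early CBC on Day 5 would leave Days 6 and 7 unmeasured.
2. Keep Day 7 as the limit for all clinical and hematologic DLTs. Add one sentence to the DLT definitions in the synopsis, Section 6.5.2 and Section 11. Suggested text: A new Grade 3 or higher chemistry abnormality on the Day 8 visit sample counts as occurring within the DLT window; a Grade 3 or higher electrolyte value is repeated just over 24 hours later to establish persistence.

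The cost is edits in six places and one extra tube per patient: 9 in stage 1 and at most 20 in all. It adds an occasional repeat sample, and an occasional separate draw when the CBC was taken before Day 7. No extra routine visit is added. The window lengthens by up to 2 days (9 − 7), for laboratory-based DLTs only. The documents do not state enrollment status; the change helps only patients not yet dosed.

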### 6.5.3 Stopping Rules

IMG-7289 will be discontinued in the event of the following:

- Post DLT, the Investigator deems it unsafe for the patient to continue on IMG-7289.
- Post dose reduction due to DLT, the patient either worsens at any time or fails to demonstrate significant improvement within 14 days.
- Post temporary interruption of IMG-7289 due to platelet counts below  $50 \times 10^9/L$  (50,000/ $\mu L$ ), the patient's platelet counts don't return to  $> 150 \times 10^9/L$  (150,000/ $\mu L$ ) within 21 days.
- Any Grade 4 non-hematologic adverse event with failure to recover to Grade 3 within 7 days of drug cessation.

Patients who discontinue IMG-7289 will enter follow-up assessments beginning with EoT visit.

